12.3. Secondary Outcomes

Preliminary estimates of efficacy. We will examine the within- and between-group effects on both efficacy outcomes (i.e., sexual risk, ART adherence) and potential mediators (mindfulness, perceived stress, depression, impulsivity, alcohol use). We will use intent-to-treat analyses, as well as per-protocol analyses to fully understand the data we obtain from this exploratory clinical trial. We predict an intervention condition x time interaction such that, relative to AC recipients, MT recipients will increase mindfulness and adherence, and decrease perceived stress, depression, impulsivity, and sexual risk behavior over time. We do not expect to see changes in VL or STIs at the follow-up, because this is too brief an interval to expect changes. Using a series of longitudinal mixed effects models, we will simultaneously regress outcomes (efficacy measures and mediators) at end of intervention and follow-up, on condition (MT vs. AC), time, condition x time, baseline value of the outcome and potential confounders of the intervention effect (including variables not balanced by randomization). Models will include a subject-specific intercept to account for within-subject correlation in the outcome over time. Modeling will be done using a likelihood-based approach and thus will make use of all available data (on the intent-to-treat sample) to produce consistent estimates of the regression parameters. Models require specification of the distribution of the outcome and will be adapted for continuous, binary, and count variables. Models will allow us to estimate the average change over time within condition for efficacy outcomes and potential mediators, as well as estimate the effect size with respect to between group effects.

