2.2 Study Rationale

Mindfulness training can reduce perceived stress, depression, and impulsivity.

Mindfulness has been defined as the act of paying attention to the present moment's experience in an intentional and non-judgmental way.³⁶⁻³⁸ While mindfulness is a fundamental ability of the mind, studies have shown that mindfulness levels increase with training, thus showing that mindfulness is also a teachable skill.⁷⁴ The best known program is Mindfulness Based Stress Reduction (MBSR),⁷⁵ which offers training in traditional mindfulness meditation adapted to a non-Buddhist, clinical context. The MBSR program has been shown to be effective in reducing anxiety, depression, and a variety of physical symptoms in many medical conditions⁷⁶⁻⁷⁸ including cancer,⁷⁹⁻⁸² chronic pain,^{83,84} rheumatoid arthritis,⁸⁵ and fibromyalgia.⁸⁶

Current evidence suggests the efficacy of mindfulness training (MT) on the aforementioned barriers to adherence in the HIV context. First, MT improves depressive symptoms and perceived stress, with moderate to large effect sizes. Hofman et al.⁸⁷ reviewed 39 studies where

patients received MT for a range of psychiatric or medical conditions and reported that MT led to robust and sustained improvements in mood symptoms (Hedge's $g = 0.95$). The Campbell Collaboration⁸⁸ reviewed 31 RCTs, and found medium-sized post-intervention effects for depression ($g=0.54$) and for stress/distress ($g=0.56$). Goyal et al.⁸⁹ included 47 randomized clinical trials and found improvements in depression at 8 weeks that lasted up to 6 months. The most recent meta-analytic study⁹⁰ isolated results from 12 studies that included only participants diagnosed with a current episode of a depressive or anxiety disorder, and found significant benefits on depressive symptom severity for MT relative to controls.

[figure not shown]

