4.3. Expected Benefits

The proposed research may result in direct benefits to participants and we expect that these benefits will outweigh the minor risk associated with participating in this research study. Individuals who complete the mindfulness training may experience reduced levels of distress, depression, and impulsivity; and an improved quality of life. Individuals who complete the general health intervention may improve their health behaviors. The magnitude of the benefits may be mild to moderate, and such benefits may last for the duration of the intervention and likely for the following months. Participants may also benefit from receiving additional medical assessments (e.g., sexually transmitted infection testing). By participating in the research, participants will also benefit from knowing they may ultimately be helping others to reduce their risk behavior, adhere better to their HIV treatments, and improve their health.

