7.1. Study Outcomes

Primary outcomes: feasibility and acceptability.

Feasibility: Key metrics will include the number of screened, eligible, consented and randomized participants; retention rates; session attendance; and individual mindfulness practice. We will consider either condition feasible under the following conditions:

- 1) If we achieve retention rates of 80% at the final follow-up visit
- 2) If patients attend at least 70% of the planned sessions
- 3) If patients report to have completed 70% of the assigned individual home practice exercises
- 4) Intervention session calls lasting approximately 20 minutes
- 5) Fewer than three rescheduled intervention calls

Acceptability: We will assess the following domains:

- 1) Participants' experience in the study (qualitative data collection)

- 2) Participants' ratings of the interventions on a satisfaction survey. The intervention will be considered acceptable if ≥80% of participants responds that they are at least somewhat satisfied with the intervention.

Secondary outcomes:

Preliminary estimates of effect size of mindfulness training vs. attention control on changes from baseline ART adherence, risky sex behaviors as well as on hypothesized mediators (i.e., mindfulness, depression, perceived stress, and impulsivity) will be assessed. We expect that the mindfulness training condition will achieve larger positive changes in ART adherence and risky sexual behaviors compared to the attention control condition.

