7.2. Design Overview

Participants ($n = 50$; 25 per condition) will be assessed (i.e., baseline), randomized to intervention (i.e., 8 weekly phone-delivered sessions of mindfulness training or the attention control intervention), and reassessed at the end of the intervention (i.e., post-intervention), and at 3 month post-intervention follow-up.

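### Section 12.3 predicts the mindfulness benefit as a condition x time interaction, but in the model it specifies that term measures durability, and the contrasts that do measure the benefit are not named

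*Combined protocol and SAP*

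**What the plan says.** Section 7.1 sets the secondary target as "Preliminary estimates of effect size of mindfulness training vs. attention control on changes from baseline ART adherence" and the other secondary measures. It expects that the "mindfulness training condition will achieve larger positive changes in ART adherence and risky sexual behaviors" than AC. The target is therefore a between-arm difference in change from baseline.

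Section 7.2 has participants assessed at baseline, randomised, and "reassessed at the end of the intervention (i.e., post-intervention), and at 3 month post-intervention follow-up". Neither of the two later visits falls before or during treatment.

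Section 12.3 first gives the prediction: "We predict an intervention condition x time interaction such that, relative to AC recipients, MT recipients will increase mindfulness and adherence", with matching decreases in stress, depression, impulsivity and sexual risk. It then gives the model, a mixed model with a subject-specific intercept, fitted to outcomes "at end of intervention and follow-up, on condition (MT vs. AC), time, condition x time, baseline value of the outcome" and potential confounders. It ends by saying the models will "estimate the effect size with respect to between group effects", without naming a coefficient, contrast or visit.

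**The concern.** The prediction and the model do not fit together. A condition x time interaction captures differential change from baseline when baseline is one of the responses. In 12.3 baseline is on the right-hand side, and the only time step left is from post-intervention to follow-up. The interaction then asks whether the MT effect changes after treatment ends, not whether there is an effect.

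This matters because the protocol's own text leans towards lasting effects. Section 4.3 says "such benefits may last for the duration of the intervention and likely for the following months", and section 2.2 cites a review that "found improvements in depression at 8 weeks that lasted up to 6 months". If that pattern occurs, the one term linked to the prediction is centred on zero. Section 12.6 uses these estimates to judge whether MT effects look encouraging, so an analyst who follows the prediction literally could report no effect, or an adverse one, when the same fit shows a benefit.

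**Working it through.** The plan gives no effect size, SD, correlation or alpha for these outcomes, and section 12.6 bases n = 50 on practical considerations, so there is no planned figure to reproduce. The structural result needs no assumed numbers; the illustration does.

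**Structure.** Code time t = 0 at post-intervention and 1 at follow-up, and score outcomes so that positive favours MT. The 12.3 model is

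E[Y_t] = b0 + b1·MT + b2·t + b3·MT·t + b4·Y_baseline.

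- Baseline-adjusted MT-AC contrast at post-intervention: b1
- At follow-up: b1 + b3
- Average of the two: b1 + b3/2
- Condition x time: b3 = follow-up contrast − post contrast

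So b3 is zero for a sustained benefit, negative for a fading one, and positive only if the benefit grows after treatment.

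**Check by fitting.** The 12.3 random-intercept model was fitted to large simulated data sets (4000 per arm, all correlations 0.5).

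| True effect, post / follow-up | Condition (b1) | Condition x time (b3) |
|---|---|---|
| 0.5 / 0.5 | 0.49 | 0.00 |
| 0.5 / 0.25 | 0.49 | −0.25 |
| 0.5 / 0 | 0.49 | −0.50 |
| 0.25 / 0.5 | 0.24 | 0.25 |

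With baseline as a third response, the first scenario gives interaction terms of 0.47 and 0.47. The prediction therefore fits a three-wave model, not the one written.

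**Size at 25 per arm.** Inputs: n = 25 per arm (sections 3, 5.1, 12.6). Assumed: SD 1, correlation with baseline rb = 0.5, correlation between the two later visits rv = 0.6, complete data.

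- SE(interaction) = √(4(1 − rv)/n) = √(1.6/25) = 0.253
- SE(averaged contrast) = √(2((1 + rv)/2 − rb²)/n) = √(1.1/25) = 0.210
- SE(single-visit contrast) = √(2(1 − rb²)/n) = √(1.5/25) = 0.245

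Multiplying by t(0.975) ≈ 2.01 gives 95% half-widths of 0.51, 0.42 and 0.49.

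| Scenario (SD units) | Interaction | Contrast from the same fit |
|---|---|---|
| Sustained 0.5 | 0.00 ± 0.51; adverse sign in 50% of trials | averaged 0.50 ± 0.42; favourable in Φ(0.5/0.210) = 99% |
| Fading 0.8 to 0.4 | −0.40 ± 0.51; adverse sign in Φ(0.4/0.253) = 94% | post 0.80 ± 0.49 |
| Growing 0.3 to 0.6 | +0.30 ± 0.51 | follow-up 0.60 ± 0.49 |

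If the sustained benefit were tested at two-sided 0.05 (illustration only; the plan sets no such test), the interaction would be significant 5% of the time, its type I error rate, and the averaged contrast 65% (noncentral t, 47 df). For rb of 0.3, 0.5, 0.7 and rv of 0.4, 0.6, 0.8, the averaged contrast ranges from 49% (0.3, 0.8) to 87% (0.7, 0.6); with 20 per arm, from 40% to 79%. The pair (0.7, 0.4) is left out because the residual covariance, 0.4 − 0.49 = −0.09, cannot arise from a random intercept.

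**Dropout.** In 4000 simulated trials of the 12.3 model with 20% random dropout at follow-up, the sustained case gave interaction 0.00 (significant in 5.1%) and averaged contrast 0.50 (61.4%). The fading case gave interaction −0.41, negative in 92.6%.

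**Counts.** A random-intercept Poisson model was simulated with a sustained rate ratio of 0.6, 25 per arm, mean 5 before a log-normal frailty (SD 0.8, correlation 0.5 with baseline) and log(baseline + 1) as covariate. The interaction ratio was 1.00 and the averaged ratio 0.61.

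**The case against.** The strongest reply is that this is loose wording in an exploratory analysis. Section 12.2 says the study is not powered for treatment effects and any testing is exploratory; no decision rule uses the interaction. Section 12.3 also promises within- and between-group effects, section 7.1 states the target as change from baseline, and nowhere is the interaction called the effect size to report. A sensible analyst could read the prediction as differential improvement since baseline and report the right contrasts. All of this limits the consequence. It does not remove the mismatch: the only coefficient tied to the expected benefit does not measure the 7.1 target, and the general promise of between-group effects leaves post, follow-up, average and interaction all open.

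Three narrower points have some force.

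- The support for durability is indirect. Section 4.3 covers the benefits of both interventions, and the review in section 2.2 concerns depression. Neither predicts a sustained MT-AC difference in adherence or sexual risk. But fading and growing effects are also misread by the interaction.
- Sexual behaviour is recalled over three months (section 8.3), so the window at post-intervention includes about 3 to 5 weeks before treatment. Assuming a 13-week window and a rate ratio of 0.6 that starts between session 1 and mid-course, the post ratio is diluted to about 0.69 to 0.88. The interaction ratio is then about 0.68 to 0.87, in MT's favour. The count illustration is therefore not representative of that measure, although the interaction still differs from the 0.6 benefit.
- Laboratory STI is scheduled only at baseline and follow-up (Table 8.2), so it has no post or averaged contrast. It is not among the outcomes in the predicted interaction, and those that are have both visits.

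**Conclusion.** The concern holds. In the model of section 12.3, condition x time is the change in the MT-AC difference from post-intervention to follow-up; this is algebra and rests on no assumption. Read as the predicted benefit, it would be null for a lasting effect and adverse for a fading one. In the illustration it is 0.00 ± 0.51 against an averaged contrast of 0.50 ± 0.42. Those sizes depend on the assumed effects, SD and correlations, because the documents supply none.

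The model is valid and already yields the needed estimates. The defect lies in the term attached to the prediction and in the missing name for the effect-size contrast. It is worth correcting, but its reach is limited to exploratory secondary estimates and what they suggest for the planned larger trial. The primary feasibility and acceptability outcomes are unaffected.

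**What to change.** Amend section 12.3 as follows, keeping the model:

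1. State the prediction as baseline-adjusted MT-AC contrasts at post-intervention, at follow-up, and their average, each with a 95% CI and on the link scale for binary and count outcomes.
2. Name these contrasts as the between-group effect sizes. For an outcome not measured at post-intervention, use the follow-up contrast alone.
3. Describe condition x time as the durability of the effect.
4. Derive within-condition change from baseline as the model-adjusted mean at each visit minus the baseline mean, since the model's own time term covers only post-intervention to follow-up.

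Moving baseline into the responses would also make the interaction wording meaningful, but it is a different model and is not needed. With only a random intercept it would force equal correlations among all three visits, and for binary and count outcomes it is not interchangeable with adjusting for baseline.

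The cost is a wording change in 12.3, with the same data, model and software.

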12.4. Qualitative Analyses

Audio recordings of the patients' interviews will be reviewed and summarized in a framework matrix. [name] and a second rater will listen to and summarize the audios. NVivo software will be used to manage the framework matrix and the audio. Throughout the coding and analysis process, categories and subcategories will be compared and revised as new information is considered or as the team comes to new understandings of the data.

12.6. Sample Size

Because effect size estimates based on small samples have large SDs and wide confidence intervals (CIs),¹⁸⁴ we will use these pilot data only to gauge whether MT effects are encouraging, to examine distribution of the outcomes, and to inform future analytic approaches. The choice of the proposed sample size ($n = 50 - 25$ participants per condition) was based on practical considerations.

12.7. Missing Data

As noted earlier, the primary analysis will be performed according to the intention to treat approach. Withdrawals will be asked to complete follow-up assessments and home visits or phone interviews will be arranged if necessary. If we encounter substantial missing data, possible options will include using accepted statistical methods (e.g., use of complete data only, use of multiple imputation, use of modified weights and model-based procedures).

13. REGULATORY REQUIREMENTS

13.1 Institutional Review Board (IRB) Review

This protocol and any subsequent modifications will be reviewed and approved by the IRB at TMH responsible for oversight of the study.

13.2 Informed Consent and HIPAA

Consent will be obtained at the screening visit. Individuals will provide written consent using an IRB approved consent form. In addition to describing the study and the participant's involvement in detail, the consent form also emphasizes that participation is voluntary, that consent may be withdrawn at any time, and that participants may withdraw from the study verbally or in writing by contacting the study RA and/or the PIs. Participants are given ample opportunity to ask questions before providing consent. Contact information for the PIs as well as the IRB (for complaints) is provided in the consent form. Signed informed consent forms will be kept in locked filing cabinets separate from all data. Participants will receive a copy of the consent and HIPAA document for their records.

13.3 Participant Confidentiality

Protection of Participant Privacy: All phone contacts with the participants will take place in a private, locked office and will be conducted by the PD who has been trained and certified in the protection of human subjects in research trials and HIPAA requirements according to TMH policies. Individuals who are interested in the study will provide Contact Information (e.g., name, address, phone, email) and will be scheduled for a screening visit (screening visit 1) to learn more about the study requirements and procedures, and to sign written informed consent as approved by TMH Institutional Review Board (IRB).

In addition, because of the potentially sensitive nature of the data we are collecting, we will apply for a **Certificate of Confidentiality** for this study to ensure that participants' data cannot be subpoenaed with a court order. We have successfully obtained Certificates of Confidentiality for other, similar research projects.

Because some of the qualitative assessments involve participation in focus groups with multiple participants, it is impossible to guarantee privacy of information that is shared in a group format. However, at the beginning of each focus group, a statement will be read to participants regarding maintaining the privacy of information shared in the group. In addition, participants will be reminded of these instructions and to respect each other's privacy and not repeat information shared with the group outside of the study setting at the start of each focus group.

Data Safety

- Participants will be identified with a randomly generated identification code unique to the participant and all personal identifiers will be removed from the study questionnaires and from datasets. Electronic communication with outside collaborators will involve only unidentifiable information. AE reports and annual summaries will not include participant-identifiable material.
- Data collected for screening (i.e. reasons for ineligibility and refusal) and tracking reasons (Filemaker data base) that contain identifiers will be stored into a password-protected server separate from other study data and will be destroyed at study completion. This Filemaker database is password accessible only to the PD, the data systems analyst, and the PI.

- Signed consent forms will be stored in locked filing cabinets separate from all other study data.
- Audio files from qualitative data collection will have no identifiers and will be destroyed following approval of the summarization.
- Patients will be informed in the consent form that the instructors' voice during mindfulness sessions will be digitally recorded for assessments of treatment fidelity and digital recordings will be treated as explained above for focus groups recordings.
- All copies of de-identified study questionnaires (paper and/or electronic) will be destroyed at the earlier of two dates: 1) seven years after the end of the study; 2) after the manuscript based on the work is published.

